2.9 Translational opportunities

Pre-clinical and clinical data suggest that combination of immune checkpoint inhibitors targeting non-overlapping pathways such as durvalumab and tremelimumab may induce synergistic effect leading to improved tumor response in comparison to monotherapy with either agent alone. We hypothesize that the combination of radiation and dual immune checkpoint blockade with durvalumab plus tremelimumab may have synergistic effect on effector T cell activation ([Pardoll 2012](#)).

This study serves as a platform allowing for detailed assessment of the mechanisms of immune stimulation, predictive markers of response or resistance and rational development of the next generation of combination immunomodulatory interventions ([Taube 2014](#), [Topalian 2012](#)). Samples will be collected that may be used in post-hoc analyses including but, not limited to:

- peripheral lymphocytes analysis for immune cell gene expression and quantitative changes of lymphocyte subpopulation and immune-related cells.
- collection of tumor tissues from unirradiated tumor sites prior to radiation and after two cycles of therapy for further analysis of immune response in tumor.
- analysis of gene expression related to immune checkpoint pathways.
- analysis of frequency of mutation-associated neoantigens in tumor tissues.

3.0 **STUDY AIMS AND ENDPOINTS**

3.1 **Primary aim and endpoint**

Aim: To determine the efficacy of the dual immune checkpoint blockade with durvalumab plus tremelimumab following a small dose of hypofractionated palliative radiation in patients with MSS mCRC who have progressed on chemotherapy.

Endpoint: Overall objective response rate (ORR) as measured by RECIST 1.1 criteria.

3.2 **Secondary aims and endpoints**

3.2.1 ***Clinical benefit rate***

Aim: To determine objective tumor decrease and stable disease (SD) at 16 weeks.

Endpoint: Measurement of disease status by continuous tumor measurement (any partial response [PR], any complete response [CR] and SD at 16 weeks).

3.2.2 ***Duration of response***

Aim: To determine the duration of response of mCRC to study therapy.

Endpoint: Measurement of time from study entry until documentation of progression as determined by RECIST 1.1.

3.2.3 ***Safety and Toxicity***

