11.2 Response criteria

11.2.1 *Evaluation of target lesions*

- *Complete response (CR)*
Disappearance of all target lesions
- *Partial response (PR)*
At least a 30% decrease in the sum of the of LD of target lesions, taking as reference the baseline sum LD

- *Progressive disease (PD)*
At least a 20% increase in the sum of the LD of target lesions, taking as reference the smallest sum LD recorded since baseline or the appearance of one or more new lesions
- *Stable disease (SD)*
Neither sufficient shrinkage to qualify for PR nor sufficient increase to qualify for PD, taking as reference the smallest sum LD since baseline

11.2.2 *Evaluation of non-target lesions*

- *Complete response (CR)*: disappearance of all non-target lesions,
- *Incomplete response/stable disease (SD)*: persistence of one or more non-target lesion(s).
- *Progressive disease (PD)*: Appearance of one or more new lesions and/or unequivocal progression of existing non-target lesions.

11.2.3 *Evaluation of best overall response*

The best overall response is the best response recorded from the start of the treatment until disease progression/recurrence (taking as reference for progressive disease the smallest measurements recorded since the treatment started).

Refer to [Table 8](#) for a summary of the criteria that contribute to the determination of response.

Table 8. Determination of response

Target Lesions	Non-Target Lesions	New Lesions	Overall Response
CR	CR	No	CR
CR	Incomplete response/SD	No	PR
PR	Non-PD	No	PR
SD	Non-PD	No	SD
PD	Any	Yes or No	PD*
Any	PD	Yes or No	PD*
Any	Any	Yes	PD*

*Confirmation of PD in a patient with new lesion(s) or suspected tumor flare is required as outlines in [Sections 11.2.1](#) and [11.2.2](#).

11.3 **Symptomatic deterioration**

Patients with a global deterioration of health status requiring discontinuation of treatment without objective evidence of disease progression at that time should be reported as "symptomatic deterioration." This is also true for "symptomatic deterioration" after therapy is completed. Every effort should be made to document objective progression even after discontinuation of treatment.

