3.3 Definition of Analysis Populations

3.3.1 Intent-to-Treat Population (ITT)

The Intent-To-Treat population (ITT) will consist of patients who complete both Cycle 1 and Cycle 2, and undergo the first restaging scan after Cycle 2 for the determination of tumor response will be determined as evaluable. Non-evaluable patients will be replaced.

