6.3 Deaths

The number of deaths will be tabulated together with the primary cause of death. The details of the 'other will be included in the listing.

7. Efficacy Analysis

The efficacy analyses will use data from tumor assessments for all subjects at baseline and then after every 2 cycles (8 weeks) of treatment. The overall response to the treatment is classified as Complete Response (CR), Partial Response (PR), Stable Disease (SD) or Progressive Disease (PD) and is recorded in the eCRF at each tumor assessment.

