7.2.1 Clinical Benefit Rate

CBR is defined as the proportion of patients with no progression or death at 16 weeks.

The 95% confidence interval of the CBR will be reported using exact method based on the binomial distribution (Clopper-Pearson method). The denominator will be the number of patients in the ITT population.

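### SAP 7.2.1 defines clinical benefit as the absence of progression or death rather than SD measured at 16 weeks, so a patient who stops for symptomatic deterioration can count as a benefit

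*Combined protocol and SAP*

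**What the plan says.** The two documents define the clinical benefit rate (CBR) differently.

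- Protocol 3.2.1 is positive and measurement-based: "Measurement of disease status by continuous tumor measurement (any partial response [PR], any complete response [CR] and SD at 16 weeks".
- SAP 7.2.1 is negative: "CBR is defined as the proportion of patients with no progression or death at 16 weeks". It asks neither for a week-16 scan nor for continued treatment.
- SAP 3.5 nevertheless reports no change from the analyses planned in the protocol.

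Protocol 11.3 gives a separate reported status to a patient with "global deterioration of health status requiring discontinuation of treatment without objective evidence of disease progression at that time". It adds: "Every effort should be made to document objective progression even after discontinuation of treatment". It gives no rule for the case where progression is never documented.

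The SAP does not mention this status. In SAP 7, "The overall response to the treatment is classified as Complete Response (CR), Partial Response (PR), Stable Disease (SD) or Progressive Disease (PD"), and no title in the SAP's lists of tables and listings names symptomatic deterioration.

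The CBR denominator is the SAP's ITT set, which is "patients who complete both Cycle 1 and Cycle 2, and undergo the first restaging scan after Cycle 2"; other patients are replaced (SAP 3.3.1). SAP 7.2 describes the secondary endpoints as descriptive only.

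**The concern.** A negative definition turns lack of information into success. A patient may have SD at the first restaging scan, stop treatment some weeks later because of global decline, and be alive at week 16 without another scan. That patient has no recorded progression and no death, so SAP 7.2.1 counts a benefit. The protocol endpoint asks for SD at 16 weeks, and nothing was measured then.

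The first-listed secondary endpoint could therefore include patients who stopped because they were doing badly, and a reader of the report could not tell. With at most 21 patients, one or two such cases visibly change the reported percentage.

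**Working it through.** **1. Timing.** Protocol Table 2 schedules lesion measurement after Cycles 2 and 4 and after every even cycle from then on. Cycles last 28 days. First scan: 2 × 28 = 56 days, week 8. Second scan: 4 × 28 = 112 days, week 16. The post-treatment follow-up column of Table 2 has no lesion measurement.

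**2. The two definitions applied to the possible cases.**

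| Patient | Protocol 3.2.1 | SAP 7.2.1, literal |
|---|---|---|
| Declines before the first restaging scan | Not evaluable, replaced | Not in the ITT set, replaced |
| SD at week 8, stops for decline, PD documented by week 16 | No benefit | No benefit |
| SD at week 8, stops for decline, dies by week 16 | No benefit | No benefit |
| SD at week 8, stops for decline, scan at week 16 shows SD | Benefit | Benefit |
| CR or PR at week 8, then stops for decline, no progression or death by week 16 | Benefit (any CR or PR counts) | Benefit |
| SD at week 8, stops for decline, alive at week 16, not scanned again | Does not clearly qualify | **Benefit** |

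Among these cases the definitions part only in the last row.

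**3. The plan's own figures.** The documents give no number for CBR. Their design figures concern ORR (protocol 14.2: stop at 0 of 12 responses, accept at 3 or more of 21, with ORR 0.05 against 0.20), and they reproduce:

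- Early termination: 0.95^12 = 0.540 (stated 0.54)
- Expected sample size: 12 + 9 × (1 − 0.5404) = 16.14 (stated 16.14)
- Type I error: 0.0804 (stated 0.080)
- Type II error: 0.1967 (stated 0.197)

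None of these uses CBR.

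**4. Effect on CBR.** Each patient in the last row of the table adds 1/n: 1/21 = 4.8 percentage points at full size, or 1/12 = 8.3 if the trial stops at stage I. The base counts below are assumptions for illustration. Limits are exact 95% Clopper-Pearson, as in SAP 7.2.1: lower limit Beta(0.025; x, n − x + 1), upper limit Beta(0.975; x + 1, n − x).

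| Miscounted | n = 21, 4 true benefits | n = 12, 2 true benefits |
|---|---|---|
| 0 | 4/21 = 19.0% (5.4 to 41.9) | 2/12 = 16.7% (2.1 to 48.4) |
| 1 | 5/21 = 23.8% (8.2 to 47.2) | 3/12 = 25.0% (5.5 to 57.2) |
| 2 | 6/21 = 28.6% (11.3 to 52.2) | 4/12 = 33.3% (9.9 to 65.1) |
| 3 | 7/21 = 33.3% (14.6 to 57.0) | not shown |

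**The case against.** The strongest reply is that the SAP is silent on such patients and does not instruct anyone to count them as benefits. SAP 7 says that efficacy analyses use tumor assessments, and SAP 3.5 says that nothing departs from the protocol, so an analyst could read 7.2.1 in the light of protocol 3.2.1 and require SD at week 16. That is a fair reading, but it needs the analyst to set aside the sentence that defines the endpoint. The operative text gives the other answer.

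The protocol also has safeguards. Section 11.3 asks for every effort to document progression after stopping, 8.2.2 asks for the Table 2 assessments after early discontinuation, and 12.4 asks that data continue on the study schedule. These reduce the number of cases. They do not remove them, because the Table 2 follow-up column has no lesion measurement and no rule covers progression that is never documented.

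Three stronger readings are tempting, and the documents do not support them.

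- **That the problem is separate from missing scans.** It is not in practice. A declining patient who is scanned at week 16 has either PD or measured non-progression. The miscount needs a missing or uninformative assessment.
- **That its frequency follows from the 5-month median survival on best supportive care (protocol 2.1).** With exponential survival, that median gives 1 − 2^(−112/(5 × 30.4375)) = 0.400 dead by week 16 (0.273 and 0.225 for assumed medians of 8 and 10 months). Those deaths already count as failures. The figure is also not conditioned on reaching the week-8 scan, so it does not estimate the number miscounted.
- **That duration of response is lengthened because responders are censored at deterioration.** SAP 3.4 and 7.2.2 contain no such censoring rule, and later progression or death remains an event.

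**Conclusion.** The point holds in a limited form. The SAP's CBR definition departs from protocol 3.2.1 and, taken literally, counts as benefit a patient with SD at about week 8 who stops for symptomatic deterioration and reaches week 16 alive with no documented progression.

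The size is 4.8 percentage points per patient at n = 21 and 8.3 at n = 12. The number of such patients is unknown: the documents give none, and the counts worked through above are assumptions. The effect is confined to patients who decline between the first restaging scan and week 16, without documented PD and without an earlier CR or PR. CBR is descriptive and the go/no-go rule rests on ORR alone, so the trial's conclusion is not at risk.

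A reader might infer that every symptomatic deterioration by week 16 should be a failure. Protocol 3.2.1 does not support that: it counts any CR or PR, and protocol 11.3 requires the status to be reported without calling it a treatment failure.

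**What to change.** Restate SAP 7.2.1 to match protocol 3.2.1, for example:

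> Clinical benefit is a documented CR or PR, or SD documented at the week-16 assessment. A patient without a CR or PR who is reported with symptomatic deterioration on or before week 16, or who has no week-16 assessment showing non-progression, is counted as not having clinical benefit and stays in the denominator.

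The clause on symptomatic deterioration takes precedence over an SD scan at week 16. That goes a step beyond the protocol text, so the sponsor should adopt it knowingly; the clause on the missing assessment resolves most of the problem by itself.

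Report the number of patients with symptomatic deterioration in Table 05.03. Table 05.01 is not the place: every patient in the SAP's ITT set has a restaging scan, and in the case at issue the best response is SD. Optionally, add a sensitivity analysis of duration of response that counts symptomatic deterioration as an event, accepting that responders will be few.

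The cost is a few sentences in a SAP still marked as a draft, and a check that the eCRF captures the status, since SAP 7 describes only CR, PR, SD and PD being recorded. The reported CBR may be slightly lower. Alignment can also work the other way: a patient with a PR at week 8 and progression by week 16 is a failure under the SAP wording but a benefit under the protocol's.

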7.2.2 Duration of Response

DOR is defined as the time (in months) from best response to progression, censoring, or death) among patients with a response.

The median and a 95 % confidence interval of DOR will be reported using Kaplan-Meier methods.

8. Exploratory Translational Studies

Immune markers will be explored by NSABP out of the scope of this SAP.

9. Appendices

Appendix 1: List of Statistical Tables

Appendix 2: List of Data Listings

Appendix 1: List of Statistical Tables

Table Number	Table Title	Population
Table 01.01	Patient Disposition	All enrolled patients
Table 01.02	Completion Status and Discontinuation from study drugs	ITT
Table 01.03	Completion Status and Discontinuation from the Study	ITT
Table 02.01	Demographic and Other Baseline Characteristics	ITT
Table 03.01	Extent of Exposure	ITT
Table 04.01	Summary of Adverse Events	Safety
Table 04.02	Grade 1/2 Adverse Events by SOC and PT	Safety
Table 04.03	Grade 3/4 Treatment-Emergent Adverse Events by SOC, PT	Safety
Table 04.04	Adverse Events Leading to Discontinuation of Study Therapies, by SOC and PT	Safety
Table 04.05	Fatal Adverse Events by SOC and PT	Safety
Table 04.06	AEs leading to Death by SOC and PT	Safety
Table 04.07	Deaths	Safety
Table 05.01	Best overall response	ITT
Table 05.02	Objective Response Rate	ITT
Table 05.03	Clinical Benefit Rate at 16 weeks	ITT
Table 05.04	Duration of Response	ITT
Figure 05.05	Kaplan-Meier Duration of Response Plot	ITT

Appendix 3: List of Data Listings

Listing Number	Listing Title	Population
Listing 01.01	Patient Disposition	All
Listing 01.02	Patient Completion of Study Treatment and of Study	All
Listing 02.01	Demographic and Other Baseline Characteristics	All
Listing 03.01	Study Drug Administration	All
Listing 04.01	Adverse Events	All
Listing 04.02	Serious Adverse Events	All
Listing 04.03	Fatal Adverse Events	All
Listing 04.04	Deaths	All
Listing 05.01	Tumor response (including ORR and CBR indicators)	All
Listing 05.02	Duration of Response	All
